EUC Condition: The EUC condition will involve 2 brief (5-10 minute) educational sessions delivered via telephone or video chat over the course of 4-6 weeks following study enrollment and randomization. The project therapist will review and discuss two brochures covering topics related to chronic pain and buprenorphine treatment with the participant, in addition to reviewing a study-developed resource guide. Thus, the EUC condition will provide some level of contact and education regarding relevant topics but will not overlap with the specific content of the PPMI condition. Participants will also be asked to provide feedback on the quality and relevance of the session material via a post-treatment self-report survey at follow-up.

Sample Size and Population

The target enrollment number for the RCT is 200 participants. Participants will be recruited from multiple community-based organizations and buprenorphine treatment clinics as well as the Veterans Health Administration (VHA). Of these 200 participants, 100 will be randomized to receive the PPMI condition (intervention condition) and 100 will be randomized to receive the EUC condition (control condition).

For this protocol, randomization to condition will be carried out by blocking on gender (male vs. female), past year use of heroin (yes vs. no), and veteran status (veteran vs. community). Computerized randomization will occur in blocks of randomly chosen sizes to equalize randomization over time and to prevent the possibility that staff could unwittingly manipulate subject assignment to conditions.

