9.2 Sample Size and Randomization

Sample size estimates were guided by our prior work on psychosocial interventions for pain during addiction treatment and prior trials that used MAT retention as an outcome and calculated using Stata. In studies of buprenorphine programs, retention varies widely but generally is around 50% in studies with at least 3-months of follow-up and robust sampling.²⁶ For a time-to-event analysis we assumed an event rate of 50% in EUC, where the event is dropping out of treatment, and based calculations on a two-sided $\alpha=0.05$. A hazard ratio of 0.5 (i.e., PPMI less likely to drop out of treatment) would achieve >85% power with a sample size of 200, or 100 per group. Given that we will be able to infer treatment retention even for participants who drop out of the study, our primary outcome analysis was based around our complete sample size of 200.

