For **Secondary Aim 1**, retention on buprenorphine treatment will be measured using data collected during the Time Line Follow Back over 12-months. The Timeline Follow-Back Assessment of Substance Use (TLFB) protocol examines daily alcohol and other drug consumption over specified time intervals (e.g., 90-180 days) using monthly calendars. Several studies have demonstrated the reliability and validity of this method of assessing alcohol use using test-retest and convergent methodologies, and a recent study supports the reliability and validity for assessing drug use. Utilizing the TLFB, we will be able to collect alcohol use, drug use, and buprenorphine treatment data (including number of days the participant has taken their medication) throughout the entire follow-up period (12-months post study enrollment).

The secondary outcomes are hypothesized to meet the assumptions of continuous variables, and we will consequently use t-tests to make comparisons. If, however, the distribution of a measure is skewed, alternative modeling strategies will be used. In all analyses, we will use an intent-to-treat framework. Pain level will be measured using the Numeric Rating Scale for Pain Intensity (NRS-I), an 11-point numeric rating scale (0 = no pain, 10 = worst pain imaginable). All participants will be asked to rate their usual and worst pain over a specified time frame (e.g. past week, past 3 months, since last visit, etc.) We will take the average of these ratings as the primary measure of pain intensity. Participants will complete the NRS-I during all assessments, including the weekly surveys. Frequency of substance use will be measured using the Time Line Follow Back Interview (TLFB), a calendar-assisted structured interview that provides the participant with temporal cues to increase the accuracy of recall. Participants are asked to recall how much they drank or used any other controlled substances on each day during the specified time frame, starting with the most recent day and progressing back one day at a time. The interviewer-administered instrument has demonstrated test-retest reliability of greater than 0.86. Percent days abstinent from alcohol and drugs will be used as the primary measure of substance use at

each assessment time point (baseline enrollment assessment and 3- and 12-month follow-up assessments).

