9.6 Data Analyses

This study will utilize an intent-to-treat approach where the primary analyses will examine the association between randomization to condition and the treatment outcomes, irrespective of how much of the intervention or control conditions the participants attended. However, in exploratory analyses, the study will explore how controlling for session attendance influences the primary results and whether session attendance mediates the potential effects of assignment to treatment condition on the subsequent outcomes. The PI, data manager, and project biostatisticians and/or data analysts will analyze the data using SAS software. The primary specific aims will focus on pain (level, tolerance and pain-related disability) and substance use (frequency of drug, alcohol and opioid use) outcomes. Outcome data will be analyzed using mixed model regression analyses. The alpha level will be set at 5%.

As stated previously, the primary aims are:

Primary Aim 1: Conduct a randomized controlled trial (RCT) comparing a remotely delivered PPMI (n=100) to EUC (n=100) to assess the impact of randomization to PPMI on retention on buprenorphine treatment over 3-months.

Research Hypotheses for Primary Aim 1: Participants in the PPMI condition will have greater retention on buprenorphine treatment (i.e., lower treatment dropout): up to 3-months. The primary goals for the project are to test the preliminary efficacy of an 8-session Psychosocial Pain Management Intervention (PPMI), as compared to an EUC control condition, on retention on buprenorphine treatment. We will evaluate measures of self-reported information gained from the TLFB on buprenorphine treatment use on a daily basis and data collected from weekly surveys completed by the participant. For those with multiple sources of information available (TLFB and self-report survey), we will use the comparison between sources of data to develop reasonable assumptions about actual consumption. It is anticipated that individuals will occasionally miss a day of buprenorphine treatment without having dropped out of treatment. Discontinuation of treatment will be operationalized as 7 days in a row without taking buprenorphine. Analysis will follow a time-to-event (survival analysis) framework where the outcome is time until discontinuing buprenorphine treatment.

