means and standard deviations for these outcomes at baseline, 1-, 3-, 6-, 9-, and 12-months, as well as change scores from baseline for the two groups. We hypothesize that participants randomized to the PPMI will have less pain, better functioning, and lower frequency of opioid use at follow-ups compared to EUC. These secondary outcomes are hypothesized to meet the assumptions of continuous variables, and we will consequently use t-tests to make comparisons. If, however, the distribution of a given outcome measure is skewed, alternative modeling strategies will be used. We will use a linear mixed-effects model and estimate the treatment effect as the difference in the time-averaged changes from baseline in pain levels (using the NRS-I) and in pain-related functioning (using the BPI) over the course of follow-up (namely, at 3-months for secondary aim 2 and at 12-months for secondary aim 3). Because reduction in pain is of key interest, the analysis will model change-scores from baseline in the response variable as the dependent variable, and the independent variables will include the baseline values of the response variable, time in months since randomization and the treatment group indicator. The parameter estimate of the treatment group indicator will estimate the time-averaged treatment effect. If the graphical exploration (described above) shows potentially differential linear decrease in pain over time, we will include an interaction of time by treatment group indicator to model and test for this. For frequency of substance use, we will first assess the distribution of measures collected to assess alcohol use, illicit drug use and prescription opioid medication use to determine whether a summary or composite measure of each of these may represent the use or misuse more appropriately. For example, illicit drug use will be obtained as the number of days the participant used each of multiple drugs, and thus we may consider combining the days of any of the illicit drug use. We will also combine the alcohol and drug use data obtained using TLFB interviews as the percent days abstinent from alcohol and drugs during the past 30 days at each assessment time. We will then check the distribution of the substance use and prescription medication misuse (measured using the TLFB), and unless the data are highly skewed, we will use a linear mixed-effect model to test the hypothesis and to estimate the treatment effect as the difference in the time-averaged changes from baseline in these outcome measures over the course of the 12-month follow-up period.

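### Section 9.6 prescribes both t-tests and a baseline-adjusted mixed model for the same secondary outcomes and does not say which is the inferential test

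*Combined protocol and SAP*

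**What the plan says.** Section 9.5.1 states: "The secondary outcomes are hypothesized to meet the assumptions of continuous variables, and we will consequently use t-tests to make comparisons". Section 9.6 repeats this under the hypotheses for Secondary Aims 2 and 3 ("we will consequently use t-tests to make comparisons"). Both places add that unnamed alternative models will be used if a distribution is skewed. Neither says whether the t-tests compare raw follow-up values or changes from baseline, or at which visit.

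The same paragraph of 9.6 then says, for pain level (NRS-I) and pain-related functioning (BPI): "We will use a linear mixed-effects model and estimate the treatment effect as the difference in the time-averaged changes from baseline". The dependent variable is change from baseline. The independent variables are the baseline value, months since randomisation and treatment group, and the group coefficient is the time-averaged effect. No skewness condition is attached. For substance use, 9.6 chooses a linear mixed model to test the hypothesis unless the data are highly skewed. It does not restate the baseline covariate there, and it describes only the 12-month period.

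The opening paragraph of 9.6 says generally that outcome data will be analysed by mixed model regression, and adds "The alpha level will be set at 5" per cent. No section says which result is confirmatory or that the t-tests are descriptive.

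**The concern.** Section 9.1 undertakes to plan the hypothesis tests in advance in order to limit Type I error. Here an analyst with well-behaved data can follow the text to two p-values for one hypothesis, for three outcomes over two periods. The two can disagree, and the plan does not say which one is reported as the result.

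They also answer different questions. The mixed model targets a change averaged over follow-up, while the t-test's target is left open and is naturally read as a difference at one visit. A t-test without a baseline covariate is also less precise than the adjusted analysis. At a single visit it excludes anyone missing that visit unless values are imputed, and it can be biased if missingness depends on earlier post-baseline values.

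**Working it through.** **The plan's own figure.** The only power statement is for the primary outcome (section 9.2): "A hazard ratio of 0.5 (i.e., PPMI less likely to drop out of treatment) would achieve >85% power with a sample size of 200". With 50% dropout in EUC and proportional hazards, events = 100×0.50 + 100×(1−0.5^0.5) = 50 + 29.3 = 79.3. Schoenfeld power is Φ(√(79.3/4)×ln 2 − 1.96) = 87.0%, so the statement reproduces. No power figure is given for the secondary outcomes, so the checks below rest on assumptions, labelled as such.

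**1. Do both tests apply to the same data?**

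| Outcome | t-test (9.5.1, 9.6) | Mixed model (9.6) |
|---|---|---|
| Pain level, pain-related functioning | if not skewed | no condition |
| Substance use | if not skewed | unless highly skewed |

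With unskewed data, both are prescribed in every row.

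**2. Precision at a single visit.** Assumptions not in the documents: equal variance (set to 1) at baseline and follow-up, and correlation r between them.
- Raw follow-up t-test: variance 1.
- Change-score t-test: variance 2(1−r).
- Baseline-adjusted: variance 1−r².

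The reduction from adjustment is 1 − (1−r²)/[2(1−r)] = (1−r)/2 against the change score, and r² against the raw value.

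| r | Change score | Adjusted | Cut vs change score | Cut vs raw value |
|---|---|---|---|---|
| 0.4 | 1.20 | 0.84 | 30% | 16% |
| 0.5 | 1.00 | 0.75 | 25% | 25% |
| 0.6 | 0.80 | 0.64 | 20% | 36% |

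Adjustment is more precise under either form of t-test, but the two ranges move in opposite directions with r.

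The planned model also averages over visits, with variance (1+(k−1)r)/k − r² for k equally correlated visits. At r = 0.5 this is 0.50 for two visits (1 and 3 months) and 0.35 for all five. The additional gain comes from averaging a different quantity, so the single-visit figures are the like-for-like cost of leaving out baseline.

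**3. Error rate if either test may be claimed.** Simulation with 8,000 trials per setting, 80 per arm (section 4 expects 160 of 200 to provide follow-up data; equal loss assumed), complete data, k = 2 or 5, r = 0.3, 0.5 or 0.7, two-sided 5%. The t-test is at one visit, and the model is the baseline-adjusted time average.
- No true effect: each test alone rejects in about 5% (4.5 to 5.3%).
- No true effect, either change-score t-test or model significant: 8.1 to 9.1%.
- No true effect, either raw follow-up t-test or model significant: 7.8 to 9.3%.
- True difference of 0.4 SD (assumed): the change-score t-test and the model disagree on significance in about 9 to 42% of trials.

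**4. Missing visits.** In the team's earlier trials (section 2.2), one had over 95% with data at some follow-up but 87% at 12 months, and another reached 78% at 3 months. A mixed model uses the visits a participant did attend; a single-visit t-test does not.

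**The case against.** The strongest reply is that the plan really is a mixed-model plan. The model is specified in detail and backed by the general statement in 9.6, whereas the t-test gets one undetailed sentence, stated twice. That is a fair account of the balance of the text. It also rules out a stronger reading that a reader might infer: that the t-test is the stated analysis and the mixed model only a fallback for skewed data. The mixed-model sentence for pain and functioning carries no such condition, a linear mixed model does not cure skewness, and for substance use it is the choice when data are not highly skewed. But the detail given to the model does not withdraw the t-test sentence.

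Three further points stand:
- The t-test's form is unspecified. It cannot be asserted that it ignores baseline altogether, since 9.5.2 and 9.6 plan change scores, or that it must drop participants, since 9.1 allows multiple imputation.
- The expected 20% without follow-up data does not measure the t-test's extra loss. It is not a per-visit rate, and someone with no follow-up value contributes no outcome to a change-score mixed model either.
- Bias is possible, not certain. Missingness that depends only on baseline, equally in both arms and without effect modification, leaves the difference between arms unbiased.

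**Conclusion.** The concern holds for the secondary outcomes. Sections 9.5.1 and 9.6 leave two unranked tests, with different estimands, for each hypothesis of Secondary Aims 2 and 3 when data are unskewed. If either may be claimed, the per-outcome error rate is about 8-9% instead of 5%. That figure describes what the wording permits; nothing in the documents shows an intention to choose between results. It rests on 80 per arm, complete data, equally correlated visits and correlations of 0.3 to 0.7.

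The single-visit precision cost of an unadjusted t-test is a variance reduction forgone of 20-30% (change score) or 16-36% (raw value) at correlations of 0.4 to 0.6. Those correlations and the equal variances are assumptions. The entry requirement of at least 4 on the NRS-I (section 4.1) could narrow the baseline spread and shift the figures for pain.

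A reader might infer that the trial's main conclusion is at risk. It is not: the primary Cox analysis and its sample size do not depend on this text.

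**What to change.** - In 9.5.1 and 9.6, delete the t-test sentence or state that the t-tests are descriptive.
- Name the baseline-adjusted linear mixed model already in 9.6 as the single inferential analysis for Secondary Aims 2 and 3. Analyse participants as randomised, including all with at least one follow-up value.
- For substance use, state the same baseline covariate and cover both the 3-month and the 12-month periods. Keep the skewness exception, with a pre-specified criterion and a named fallback model.

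The cost is SAP wording only: no new data, visits or participants. It should be settled before any unblinded analysis.

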Research Hypotheses for Secondary Aim 1: Participants in the PPMI condition will have greater retention on buprenorphine treatment (i.e., lower treatment dropout) over the entire 12-months of follow-up. The primary goals for the project are to test the preliminary efficacy of an 8-session Psychosocial Pain Management Intervention (PPMI), as compared to an EUC control condition, on retention on buprenorphine treatment. We will evaluate measures of self-reported information gained from the TLFB on buprenorphine treatment use on a daily basis and data collected from weekly surveys completed by the participant. For those with multiple sources of information available (TLFB and self-report survey), we will use the comparison between sources of data to develop reasonable assumptions about actual consumption. It is anticipated that individuals will occasionally miss a day of buprenorphine treatment without having dropped out of treatment. Discontinuation of treatment will be operationalized as 7 days in a row without taking buprenorphine. Analysis will follow a time-to-event (survival analysis) framework where the outcome is time until discontinuing buprenorphine treatment.

We will first descriptively calculate the percent still receiving buprenorphine at the 6-, 9-, and 12-month follow-ups. The independent variable of interest is an indicator of group (PPMI vs. EUC). Analysis will use an intent-to-treat framework, where participants are classified by the condition they were randomized to, regardless of what they received. Cox Proportional Hazards regression models will be used to test the association between group assignment and time to dropping out of buprenorphine treatment at 12-months. We will test if assumptions for this modeling technique are met, and if they are not, consider including a covariate*time interaction or stratification in Cox modeling, or variable transformations or alternative modeling strategies, if necessary.

Research Hypotheses for Secondary Aims 2 and 3: Compared with participants randomized to the EUC (control) condition, participants randomized to the PPMI condition will report a greater reduction in pain level, an increase in pain-related functioning, and a decrease in frequency of substance use at: (1) 3-months; and (2) 12-months post-intervention. We will calculate the

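### The secondary pain model gains a time-by-group interaction only if plots suggest it, and no treatment-effect contrast is named once it does

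*Combined protocol and SAP*

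**What the plan says.** All the relevant text is in Section 9.6, under the hypotheses for Secondary Aims 2 and 3.

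- **Outcome:** "the analysis will model change-scores from baseline in the response variable as the dependent variable".
- **Covariates:** the baseline value, "time in months since randomization and the treatment group indicator". No centring of time is mentioned.
- **Target:** the model is to "estimate the treatment effect as the difference in the time-averaged changes from baseline in pain levels" and in BPI functioning across follow-up, "namely, at 3-months for secondary aim 2 and at 12-months for secondary aim 3".
- **Named estimate:** "The parameter estimate of the treatment group indicator will estimate the time-averaged treatment effect".
- **Conditional step, which comes next:** "If the graphical exploration (described above) shows potentially differential linear decrease in pain over time", then "we will include an interaction of time by treatment group indicator to model and test for this".

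The only earlier graphical work of this kind is in Section 9.1. It is a general commitment to plot variable distributions and contains no rule for judging trends by arm. Section 9.6 does not say which quantity is the treatment effect once the interaction is in the model. The substance-use paragraph of the same section has no such step.

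**The concern.** Two things follow from the text. First, which model is fitted depends on looking at the outcome trajectories, with no stated criterion. Section 9.1 promises that tests of the main hypotheses will be planned in advance.

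Second, the two possible models give the group coefficient different meanings. Without the interaction it is the time-averaged difference, as the plan says. With the interaction, and time measured from randomization, it is the fitted difference at month 0. No session has been delivered then, and change from baseline should be near zero in both arms. That quantity answers neither aim. An analyst who follows the plan literally after adding the interaction has one named estimate, which no longer matches the stated target, and several non-equivalent replacements to choose from after seeing the curves.

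**Working it through.** **Plan figures.** The plan gives no power or precision figure for these models. Its one power statement (Section 9.2) concerns the primary Cox analysis and has no bearing here. Effect shapes, SD, correlations and trigger thresholds below are therefore assumptions.

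**Inputs from the documents.** Follow-up visits are at 1, 3, 6, 9 and 12 months (Section 9.6). Alpha is 5% (Section 9.6). About 160 participants, taken here as 80 per arm, are expected to give self-reported follow-up data (Section 4).

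**Algebra.** Write the model with interaction as

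E[change] = b0 + b1·baseline + b2·t + b3·G + b4·G·t.

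The group effect at month t is b3 + b4·t, so b3 alone is the effect at t = 0. The average over visits is b3 + b4·(mean t):

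- Aim 3, five visits: mean t = (1 + 3 + 6 + 9 + 12)/5 = 6.2, so the effect is b3 + 6.2·b4.
- Aim 2, months 1 and 3: mean t = 2.0, so the effect is b3 + 2.0·b4.
- At month 3 it is b3 + 3·b4; at month 12 it is b3 + 12·b4.

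**Growing benefit (assumed: 0 at month 0, -1.0 at month 12).** Here b3 = 0 and b4 = -1/12. The five-visit average is -6.2/12 = -0.52, the month-3 effect is -0.25 and the month-12 effect is -1.0. The group coefficient is 0.0.

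**Fading benefit (assumed: -1, -1, -0.6, -0.3, -0.1 at the five visits).** The average is -3.0/5 = -0.60. The fitted slope is 7.1/78.8 = 0.0901, where 78.8 is the sum of squared deviations of visit month from 6.2. So b3 = -0.60 - 0.0901 × 6.2 = -1.16, while the month-12 effect is -0.1.

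**Check by fitting.** A mixed model was fitted to simulated data with 2,000 per arm and a true effect of -t/12. The group coefficient was -0.569 (SE 0.048) without the interaction, -0.060 (SE 0.057) with it, and -0.569 again with the interaction and time centred at 6.2.

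**Precision (compound symmetry, correlation ρ, k visits, n per arm).**

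- Variance of the average: (2σ²/n)·[ρ + (1-ρ)/k].
- Extra variance of the month-0 coefficient: (2σ²/n)·(1-ρ)·(mean t)²/Sxx, where Sxx is the sum of squared deviations of visit month.
- With σ = 2, n = 80, ρ = 0.5 and five visits, 2σ²/n = 0.1. The average has SE √(0.1 × 0.6) = 0.245. The month-0 coefficient has SE √[0.1 × (0.6 + 0.5 × 38.44/78.8)] = 0.291.
- For ρ from 0.6 to 0.4, the month-0 SE exceeds the average's SE by 13-25% on the five-visit grid and by 41-65% on the months 1 and 3 grid.

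Under the growing benefit at ρ = 0.5, power is 5% for the month-0 coefficient, 56% for the average and 94% for month 12.

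**Type I error.** This was simulated with 400,000 null replicates per correlation, five visits and ρ from 0.3 to 0.7. A slope test at 0.05, 0.2 or 0.5 stood in for the plots. Testing the group coefficient of whichever model is selected rejects in 5.4-7.1% of trials. Counting either the group or the interaction test as a finding gives 9.7-10.6%.

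**The case against.** The strongest reply is that the sentence naming the group coefficient comes before the interaction step and is correct for the model it describes. That stands. A reader might infer that the plan commits to reporting the month-0 coefficient as the time-averaged effect, but no text says so. The target remains the difference in time-averaged change, which the interaction model can recover. The defect is that no contrast is named.

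A reader might also infer that neither model can give the 3- and 12-month effects, or that the hypotheses are only about those time points. Neither inference is supported. The interaction model yields both effects as linear contrasts, under its straight-line assumption. One sentence does place the hypotheses "at: (1) 3-months; and (2) 12-months post-intervention", but Sections 1.2 and 9.5.2 and the aims as restated in 9.6 speak of effects over 3 and over 12 months. The plan also tabulates means and change scores by group at each visit, so a growing or fading effect would be visible in the descriptive results.

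A further reply is that analysts are blind to condition (Section 6.2.3). That limits deliberate choice, but curves under masked labels still diverge visibly, so the model choice remains data-driven. A competent analyst might centre time or compute a contrast, but the plan asks for neither.

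**Conclusion.** The concern holds as a gap in specification: the model is chosen from unspecified plots, and no effect contrast is defined once the interaction enters. It concerns the secondary pain analyses for Aims 2 and 3. The trigger mentions only pain, so extending it to BPI functioning is an inference. The primary Cox analysis is untouched and no figure in the documents is wrong.

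The possible size is a reported effect of 0.0 instead of -0.52 (growing benefit) or -1.16 instead of -0.60 (fading benefit). Both depend on the month-0 coefficient being reported and on the assumed effect shapes. The 5.4-7.1% type I error is modest. It depends on the assumed trigger and on testing the group coefficient of the selected model. With complete data and compound symmetry, the time-averaged contrast has the same SE in both models (0.245 at ρ = 0.5), and the fitted check gave -0.569 both ways. Naming that contrast therefore removes most of the problem. Whether the weekly NRS-I ratings enter the model is not stated; if they do, the mean times of 6.2 and 2.0 change.

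**What to change.** Before unblinding, amend Section 9.6 as follows.

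1. Delete the plot-driven step and keep the stated time-averaged difference as the confirmatory effect.
2. Fix one model: either the main-effect model as written, or one that always includes arm-by-time (or arm-by-visit).
3. If an interaction is always included, define the effect as the average over visits. With linear time this is b3 + 6.2·b4 over the five visits for Aim 3 and b3 + 2.0·b4 over months 1 and 3 for Aim 2. State which ratings enter, and recompute the mean times if weekly ratings are used.
4. Report the month-3 and month-12 contrasts and the interaction test as supportive or exploratory.
5. Say whether the same rule applies to BPI functioning, and reconcile the *at* and *over* wording of the hypotheses.

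Making the visit-specific contrasts confirmatory, with categorical visits and unstructured covariance, is a legitimate alternative. It would replace the sponsor's stated target, however, and this problem does not require it.

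The cost is SAP wording, plus one or more extra model terms if the interaction is always included.
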